There is no problem of applying for multiple projects with the same or very similar research content as the project leader, illegally listing or occupying others research funds;

There is no illegal interference or intervention in various review activities such as scientific research projects, achievement awards, talent plans and professional title evaluation, and there is no problem of "talking" or "going through connections" in the above review activities; there is no other serious violation of scientific research integrity, scientific research ethics, academic norms and academic style.

Signature of the applicant:

Project leader	surname and personal name	[name]	sex		date of birth			
	record of formal schooling		academic degree		professional ranks and titles		post	
	work unit		Shanxi Eye Hospital			Department of residence		pharmaceutical preparation section
	ambit		pharmacy					
Partner information	name of organization							
	1.							
	2.							
	3.							

Background and basis of the project
	
(400 words limit)
 

Presbyopia (Pb), characterized by difficulty focusing clear images on the retina when viewing nearby objects, predominantly affects individuals over 40 years old and significantly impacts daily life. However, China has yet to report the approval of presbyopia treatment drugs. The theory of presbyopia accommodation mechanism suggests that human eye regulation is closely related to ciliary muscle contraction. Studies have shown that the active ingredients in the marketed drug, Sarcosin and Digitalis Glycosides Eye Drops, can synergistically enhance ciliary muscle function. These findings suggest that Sarcosin and Digitalis Glycosides Eye Drops may improve presbyopia through enhanced ciliary muscle regulation. Nevertheless, its therapeutic effects remain unreported. This study will pioneer the first validation of Sarcosin and Digitalis Glycosides Eye Drops presbyopia treatment efficacy by comparing visual quality changes between treatment and control groups. Furthermore, we will employ optometric techniques and optical scanning methods to analyze indicators including accommodation function, anterior segment OCT, and ocular perfusion data, aiming to elucidate the therapeutic mechanism. We hope this research will bridge the gap in presbyopia drug development in China.

--	--

1. Research significance and relevance to national needs:

We are currently undergoing the Fourth Industrial Revolution, which requires our visual systems to be capable of viewing and interpreting screen information from smartphones and laptops in both work and daily life, placing higher demands on near vision. With the accelerating pace of aging, presbyopia not only causes significant inconvenience in peoples daily work and life but also hinders Chinas economic development, becoming a pressing social challenge. However, there has been no reported approval for presbyopia treatment drugs in China to date. Research shows that the marketed drug, Silymarin and Digitalis Glycosides Eye Drops, contains two active components—silymarin and digitalis glycosides—which can jointly act on the ciliary muscle to effectively enhance its regulatory function. These findings suggest that Silymarin and Digitalis Glycosides Eye Drops may also improve ciliary muscle regulation to treat presbyopia. This project will, for the first time, verify the therapeutic effects of Silymarin and Digitalis Glycosides Eye Drops on presbyopia by comparing quality changes before and after treatment between the experimental group and control group. It will elucidate the therapeutic mechanism, fill a gap in current presbyopia drug research, improve patients quality of life and work productivity, and reduce economic losses caused by presbyopia.

2. Research content, new methods and technical routes to be adopted, key problems to be solved, test scale and main indicators:

【 research contents 】

(1) Changes in subjective visual quality and objective visual quality of subjects and control group before and after treatment, as well as contrast sensitivity function (CSF), diffusion function (PSF), modulation transfer function (MTF) and so on.

(2) Effects of different pupil diameters (PD) and frequency bands on higher-order aberrations (HOA) under different presbyopia conditions with different severity.

(3) Research on the influence of adjustment function and higher order aberration on visual quality and discussion on related mechanism.

(4) The dose-effect relationship between treatment course and effect under different severity of presbyopia conditions.

[Research Programme]

Research object: 30 cases of presbyopia patients who visited our hospital and met the inclusion criteria of this study.

(2) Instrumental examination. Before and after treatment: ① Measure uncorrected visual acuity under 30 lux and 180 lux conditions, including 5m uncorrected distance vision (UDVA), 80cm intermediate vision (UIVA), 30cm near vision (UNVA), and corrected vision using the same examination method after subjective refraction, including multiple measurements Far vision (CDVA), corrected intermediate vision (CIVA), corrected near vision (CNVA), DCNVA, far corrected intermediate vision (DCIVA and CSF, refractive power (D), astigmatism (DC) and so on.

② Total higher-order aberrations, spherical aberration, 慧差 and three-leaf aberration of the whole eye and lens in the frequency regions of 3c/d, 6c/d and 12~18c/d with pupil diameters of 3mm and 6mm, recording PSF and MTF. ④ OCT sweep frequency anterior pupillary diameter (PD), lens thickness (LT) and lens dome height

(LV), anterior chamber depth (ACD), anterior and posterior surface curvature, etc.

Therapeutic evaluation:

(1) Therapeutic effect and evaluation of therapeutic effect according to different severity.

(2) Calculation of the rate of removing glasses: the rate of removing glasses = the number of patients who removed glasses/total number $\times 100\%$, which is calculated to calculate the rate of removing glasses in close reading after treatment.

(3) Satisfaction assessment: Questionnaires were used to investigate and evaluate whether the subjects had visual interference symptoms and their satisfaction degree after treatment.

(4) Safety assessment: evaluate whether adverse reactions such as stinging, conjunctival congestion, photophobia, redness and so on occurred during medication. Grouping method:

Implementation of Centralized Randomized Blinding: Statistical professionals independent of the research team generate randomized allocation sequences based on study protocols. Group information is sealed in opaque envelopes. After participants are enrolled and baseline assessments completed, researchers follow procedures to open the envelopes and deblind the groups. This ensures that group assignment remains concealed during enrollment and baseline data collection phases, thereby preventing selection bias.

blind method :

Double-blind design: subjects, investigators (including efficacy assessment and data recording personnel), and statisticians were unaware

Group Information. Both drug groups use identical containers and packaging with identical dosing instructions to maintain blinding. Group information is managed by an independent third party using sealed password-protected envelopes and a central randomization system. Blinding is only lifted by the third party following

predefined protocols after data lock-up at study completion or in the event of serious adverse events. Blinding information is not disclosed to the research team.

The treatment group received a seven-leaf digitoxin total glycoside eye drop (Pharma Stulln GmbH, Import Drug Registration No.: 0909803; H20130295). Patients were instructed to use one drop in each affected eye three times daily, strictly following aseptic techniques. Care was taken to prevent contact between the dropper and the ocular surface.

[figure not shown]
The control group received an equal amount of sterile, preservative-free and non-irritating saline solution. The containers were packaged in the same appearance, specifications, and labels as the treatment group. Only the designated personnel responsible for group management in the research team knew the grouping information, while the subjects were unaware of their own group to maintain the double-blind status. Both groups received treatment for one month.

[Key issues to be resolved]

(1) The correlation between higher-order aberrations (thOA), differential spherical aberration (TSA), cloverleaf aberration (TT), and慧差 (TC) and adjustment functions such as adjustment amplitude (AMP), adjustment response (BCC), adjustment sensitivity (CPM), and positive/negative adjustment (PRA/NRA).

(2) The variation of wavefront higher-order aberration (WA) and its mechanism during the treatment.

【 technology roadmap 】

3. Expected project results (including publishing relevant papers, applying for invention patents, training talents, making contributions to the construction of academic degrees, etc.)

[Expected Research Results]

- (1) Theoretical achievements: The therapeutic effect of saponin dioscin eye drops on presbyopia was clarified, the therapeutic mechanism was elucidated, and the therapeutic effect of the same degree of presbyopia was scientifically evaluated, providing a new direction for the treatment of presbyopia.
- (2) Publication of papers: Publish 2 high-quality academic papers.
- (3) Academic conferences: Participate in one domestic academic conference.
- (4) Talent training: teach 1-2 interns.

4. Project schedule by stage (time is accurate to month)

temporal interval	The schedule of the project and the main research work to be completed
2023.12~2024.12	Continue to collect clinical subjects, complete the selection and grouping of subjects, clinical treatment and observation data collection, experimental data summary, data analysis.
2025.01~2025.12	Write and publish papers, summarize projects.

6. Project budget unit: 10,000 yuan

Budget of source of funds		Budget of expenditure	
subject	Budget figures	subject	Budget figures
Total project investment	5	Budget expenditure summary	5
(1) Application for grants	5	1. Equipment costs	
(2) Other funds		2. Material cost	0.9
		3. Test, laboratory and processing costs	
		4. Fuel and power costs	
		5. Travel costs	0.2
		6. Conference costs	0.3
		7. Collaborative research and exchange fees	
		8. Publication/literature/information dissemination/intellectual property affairs fee	0.9
		9. Labor costs	1.7
		10. Expert consultation fees	
		11. Compensation for subjects and other	1.0

		expenses	
--	--	----------	--

[figure not shown]
7. Expected social and economic benefits after the completion of the project

This groundbreaking project addresses the critical pathological mechanism where ciliary muscle regulation influences presbyopia development, while addressing Chinas current shortage of presbyopia treatment options. It establishes the feasibility of using the marketed drug Erythromycin Dihydrochloride Eye Drops for presbyopia management. This innovation not only provides a simple, safe, and effective medication selection for presbyopia treatment, alleviating the work-life inconveniences caused by myopia complications, but also significantly enhances quality of life and productivity. Furthermore, it demonstrates substantial market potential and economic value in the field.

8. Form, content and opinions of the cooperative unit

1. Forms and contents of cooperation

2. Opinions of the cooperative unit (on the content, form of cooperation, quality of participants and guarantee of working conditions, etc.) sign specific opinions:

9. Sign the task book

Project Manager (signature)

[Redacted Signature]

January 8, 2024

Opinions of project undertaking unit:

agree

Unit responsible
person
(signature)

[Redacted Signature]

[Redacted Signature]

ter
20> 4

Date: 18th

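### The allocation text has researchers open the envelopes and unblind after baseline, while the blinding text forbids this, so assessor blinding is stated but not secured

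*Protocol*

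**What the plan says.** Three parts of the protocol's research programme set rules on who learns the assignment.

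- **Grouping method.** Statisticians outside the team generate the sequence, and group information goes into opaque envelopes. The step that follows each participant's baseline is that "researchers follow procedures to open the envelopes and deblind the groups". The section gives protection against selection bias as its purpose, and claims concealment for enrolment and baseline only.
- **Blind method.** On who is kept from knowing the groups: "Double-blind design: subjects, investigators (including efficacy assessment and data recording personnel), and statisticians were unaware". Custody of the code lies with an outside third party, which uses sealed envelopes and a central system. No one else may break the blind, and the permitted occasions are data lock and a serious adverse event. On access by the team: "Blinding information is not disclosed to the research team". The two products share the same containers and packaging.
- **Control group paragraph, after the blinding text.** "Only the designated personnel responsible for group management in the research team knew the grouping information". Participants themselves stay blind under this paragraph.

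**The concern.** The trial's aim is to compare change between the eye drops and saline, and its main safeguard against expectation effects is the double blind. The allocation step as written gives group information to researchers at the start of treatment. The blinding text keeps it from them until data lock. Site staff cannot obey both.

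The exposure lies in outcomes where the examiner's conduct or judgement enters the result. The protocol lists uncorrected and corrected acuity at several distances, subjective refraction, contrast sensitivity, and adverse reactions such as conjunctival congestion and redness. It also removes cases at follow-up visits when signs of ocular surface disease are found (Subject withdrawal or termination). An examiner who knew the arm could therefore influence the measurements and also who stays in the trial. An analysis plan cannot repair a blind that was broken at allocation.

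**Working it through.** No calculation applies: the point depends on no sample size, effect size or error rate. The check is to set the rules side by side.

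| Question | Grouping method | Blind method | Control group paragraph |
|---|---|---|---|
| Who opens the code? | Researchers | The third party only | Not stated |
| When? | After each participant's baseline | After data lock, or for a serious adverse event | Not stated |
| Who in the research team knows? | The researchers who open envelopes | Nobody | Designated group-management personnel |
| What period is protected? | Enrolment and baseline | Until data lock | Not stated; subjects stay blind |

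1. **Who and when.** The first two columns exclude each other. A researcher who opens an envelope after baseline is neither the third party nor acting at data lock or for a serious adverse event.
2. **Who knows.** The second and third columns exclude each other. The research team is not told, yet some of its members know.
3. **Does a loose translation of the unblinding verb resolve it?** Suppose it means only that the assignment is revealed so that treatment can start. The envelopes hold group information and researchers open them, so the conflict with third-party custody and non-disclosure remains.
4. **Could the envelopes hold only a code?** The protocol does not say so. It mentions no kit numbers, and the containers carry the same labels in both groups. It therefore describes no route by which a researcher who does not know the arm could hand out the correct product.
5. **Are those who open envelopes kept apart from those who assess?** Nothing says so. Grouping method says only researchers, without naming a role.
6. **Which outcomes are exposed?** Directly: subjective refraction, acuity, contrast sensitivity, judgement of redness and congestion, and the ocular surface exclusions. The near-vision questionnaire, the satisfaction questionnaire and spectacle removal rest mainly on subject blinding, which the protocol states consistently. Wavefront, PSF, MTF and OCT readings come from instruments and are little exposed.

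**The case against.** The strongest reply is that the document intends a double-blind trial and is badly translated; the study drug itself appears under several names. The sentence in question sits under a passage on allocation concealment, which properly ends at assignment. On this view the designated group-management personnel open the envelopes, the assessors stay blind as the blinding text says, and there is only loose wording.

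Part of this stands. A reader might infer that the trial is in effect open-label to researchers from the start, or that its double-blind claim is false. The documents do not support that: assessors and data recorders are listed as unaware, and the people who open the envelopes may be the designated personnel. A reader might also infer that all subjective outcomes, or all measurements after baseline, are compromised. That does not follow either. The patient-reported outcomes depend mainly on subject blinding, which is consistent throughout, and the instrument readings leave little room for expectation.

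What does not stand is that the wording is harmless. The benign reading has to be supplied by the reader. It still contradicts the statement that the research team is not told, and it leaves unsaid what the envelopes contain and whether those who open them also assess.

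**Conclusion.** The contradiction is real and must be resolved, because following the allocation step as written defeats the blinding that the protocol claims. The accurate charge is that assessor blinding is stated but not secured; the document does not show that assessors are in fact unblinded.

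The consequence is conditional. If researchers open the envelopes as the allocation text says, and are not kept apart from assessment, the examiner-dependent outcomes and the ocular surface exclusions are open to bias. That could reach up to all 30 planned participants. The document gives no basis for the size of the bias, and none is claimed here. The verdict assumes only that the envelopes hold what the protocol says they hold, namely group information.

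**What to change.** 1. Delete the step in which researchers open envelopes and unblind. State instead that, after baseline, the third party or the central system already named releases only a kit number, and the researcher dispenses the identically packaged product bearing it.
2. Give each participant's supply its own number rather than a common code per arm, so that one code break does not reveal the others.
3. Keep any envelope that reveals the arm with the third party, for use only in the circumstances the blinding text already allows.
4. Reconcile the control group paragraph with the blinding text: name who holds the code, and state that anyone who knows the groups takes no part in enrolment, assessment, data recording or analysis.
5. The project schedule speaks of continuing to collect subjects, so enrolment may already have begun. If researchers have opened any envelopes, report this and do not describe those participants' assessments as assessor-blind.

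The cost is protocol wording and numbered labels, given that the third party, central system and identical packaging are already planned. The budget shows no identifiable line for the third party or the central system, so the sponsor should confirm that both are actually in place.
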